Official Study Title:

Intimate Partner Violence and Fatherhood Intervention in Residential Substance Abuse Treatment

NCT Number: NCT02979262

Date Last Modified: 3/25/2019

Data analysis Plan

Because the variables of interest involved a mix of continuous, count, dichotomous, and multinomial variables, generalized linear modeling techniques were used to test for between group differences in the demographic and clinical characteristics of the participants, the process outcomes, and the secondary outcomes only measured once or twice at the end of treatment or the end of the 3-month period of follow-up. Similarly, generalized estimating equations (GEE), the repeated-measures extension of generalized linear modeling, was used to test for between group differences in baseline values, within-group change over time, and between-group differences in the rate of change for primary and secondary outcomes measured two to five times from randomization through the 3-month period of follow-up. When there were only two measurements, time was dummy coded to represent the first and second measurements. When there were three or more measurements, time was coded as a continuous variable representing weeks from randomization. Consistent with the CONSORT recommendations, process, primary, secondary, and end-point outcomes were analyzed for both the intention-to-treat and per-protocol samples.

Across statistical analyses, dummy coding was used to represent facility and treatment assignment; and preliminary analysis of descriptive statistics, graphical representation, and goodness of fit statistics were used to determine the appropriate response distribution and link function for use in the final analysis of each dependent variable. When it was not fixed at 1.0, the deviance/df statistic was used to determine the dispersion parameter. Given the limited sample size and the potential costs of a Type II error in this type of pilot study, statistics with p values less than .10 were considered statistically significant. Despite this, there was a focus on the consistency of findings across variables and intention-to-treat versus per-protocol samples.

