Sixty fathers, their female co-parent and youngest child will be recruited to participate in the study. At the time of intake at Westcare's Emerge Program and Salvation Army's Residential Substance Abuse Rehabilitation Program, fathers will be provided flyers about the study. Men who express an interest in participating in a parenting program as part of their treatment will fill out an initial interest form with their counselors (including their name, arrival and discharge date, information about how often they're in contact with their children) and have their counselors submit this form to the Project Coordinator. The Project Coordinator will schedule a screening with the potential participant and will be asked to sign a consent form,

and to sign a release of information to review their SA treatment and criminal history. Men will be told that his questionnaire and records will be reviewed and will be contacted further if considered eligible by the PI based on the study's requirements.

This will provide the opportunity to contact the mother to conduct a phone screening in regards to IPV history and willingness to participate. If the mother indicates an IPV history that involved hospitalization or strangulation or a current full no contact protective order, he will be notified that based on the demographic screening, he is not eligible for the study. If the father is eligible and agrees to participate in the study, the research assistant will contact the father to set up a baseline assessment and the co-parent will be contacted to set up a baseline interview by phone or in-person if she wants to participate. If the father is not eligible for the program we will remove the bottom portion of his screening form that includes personal information (name, arrival and discharge date, and WestCare or Salvation Army counselor information) and shred it. The top portion including de-identified information (IPV history and contact with children) will be kept to keep track of the number of referrals compared to the number of participants in the program.

Mothers of the father's youngest child will be recruited in several ways:

1. When she visits the facility she will be approached by study staff in person.
2. She will be mailed study flyers asking her to contact the research office.
3. Westcare or Salvation Army staff will call mothers and ask permission for study staff to contact them to tell them about the study.

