Following completion of baseline assessments, subjects will be randomly assigned to the FFC intervention or the Parenting Education (Dads 'n' Kids) condition. To increase the likelihood that treatment groups are balanced with respect to demographic variables, and moderators, subjects will be assigned to treatment conditions through urn randomization using a Microsoft Access-based program. In urn randomization, an algorithm modifies ongoing randomization probabilities based on prior composition of treatment groups and maximizes multivariate equivalence of groups

Fathers in each treatment group will meet individually with their assigned therapist once per week for 50-60 minutes of treatment. The Fathers for Change Intervention has three phases: individual focused, co-parent relationship focused and restorative parenting focused. Beginning with motivational interviewing, the clinician and father will discuss child development, the impact of SA and violence on parenting, and the father's own childhood experiences of SA and violence and how he would like things to be different for his own children. The clinician will also provide skills training to reduce hostile cognitions and increase emotion regulation skills. In co-parenting focused sessions the clinician will teach communication and problem solving skills, these topics will be addressed with or without the co-parents participation. In family sessions the clinician focuses on restorative parenting to

rebuild the father-child relationship. These phases can be delivered either individually to the father or together with his children present. The decision whether family members are invited to participate will be made on a case by case basis dependent on safety of the co-parent and child, their wish to participate and their ability to come to the treatment facility.

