Table 1. Standardized Measures and administration for Randomized Trial

Instrument	Rater	Reliability	Base-line	Monthly During Intervention	Post Residential Intervention 12 weeks	Post Intervention 16 weeks	3 month follow-up 24 weeks
SA Outcomes							
Timeline follow-back for SA	Father and Mother	.91		X	X	X	X
Urinalysis Drug Panel	Father	NA	X	X		X	X
IPV Outcomes							
Conflict Tactics Scale Revised (CTS2)	Father and Mother	.79 to .95	X				X
Timeline follow-back for IPV	Father and Mother	.91		X	X	X	X
Court and Arrest Records	N/A	N/A	X				X
CM Risk Outcomes							
Parental Reflective Functioning Questionnaire (PRFQ)	Father	.82	X			X	X
Adult Adolescent Parenting Inventory (AAPI)	Father and Mother	.74 to .98	X			X	X
Father-Child Free Play coded using (CIB)+	Blind Coders						X
Quality of Co-Parental Relationship Scale	Father and Mother	F: .66 - .88 M: .80 - .83	X			X	X
Satisfaction Outcomes							
Client Satisfaction Questionnaire 8	Father	N/A				X	
Mediators							
Articulated Thoughts in Stimulated Situations (ATSS) and HR/SC	Blind Coders	N/A	X		X		
Difficulties in Emotion Regulation Scale (DERS)	Father	.93	X		X	X	X
State-Trait Anger Inventory (Staxi)	Father	.84 - .93	X		X	X	X
Rumination-Reflection Scale (ARQ)	Father	.88 - .91	X		X	X	

Working Alliance Inventory	Father and Clinician	.79 - .97		X			
Motivation to Change (URICA-DV)	Father	.85 - .87		X			
Moderators							
Childhood Trauma Questionnaire	Father	.80 - .97	X				
Self-Report Psychopathy Scale 3	Father	.60	X				
Life Change Index Scale	Father	N/A	X				X
Brief Symptom Inventory (BSI)	Father	.74 - .89	X			X	X
Addiction Severity Index	Father	.89	X				
Father Interview	RA	N/A	X			X	X
Treatment Services Review	Father	N/A				X	X
PhenX Measure: Self-Report HIV Testing	Father	N/A	X				
FRPN FATHER ENGAGEMENT SCALE_v1	Father	N/A				X	X
FRPN FATHER ENGAGEMENT SCALE_v2	Father	N/A				X	X
FRPN FATHER ENGAGEMENT SCALE_v3	Father	N/A				X	X
Measure of Contact-Fatherhood Research and Practice Network	Father	N/A				X	X
Domestic Violence Quiz	Father	N/A	X		X		
Co-Parenting Quiz	Father	N/A	X		X		

At the 3 month follow-up, fathers will be asked to attend a play assessment with their child. This will be a 30 minute appointment in which they will play with toys or games with their child for 15 minutes, clean up and then complete several puzzles with their child. These session will be audio recorded and coded using the Child Interactive Behavior Rating Scale by trained blind coders.

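### For outcomes measured at baseline and once later, the GEE lets the baseline mean differ by arm; this is unbiased but loses precision that a common-baseline constraint would recover

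*SAP*

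**What the plan says.** The SAP (Data analysis Plan) uses GEE to "test for between group differences in baseline values, within-group change over time, and between-group differences in the rate of change" for outcomes measured two to five times. For the two-measurement case: "When there were only two measurements, time was dummy coded to represent the first and second measurements". The only other model terms it names are facility and treatment assignment. It mentions neither a baseline-value covariate nor a constraint to equal baseline means. The response distribution and link are chosen outcome by outcome, and p below .10 counts as significant.

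On timing, the protocol (Study Design) says: "Following completion of baseline assessments, subjects will be randomly assigned to the FFC intervention" or the parenting education condition.

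Protocol Table 1 marks the following at baseline and exactly one later visit:
- the CTS2, and court and arrest records (baseline and 24 weeks);
- "Articulated Thoughts in Stimulated Situations (ATSS) and HR/SC" (baseline and 12 weeks);
- the domestic violence and co-parenting quizzes (baseline and 12 weeks).

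**The concern.** The SAP gives no model equation, but its three tests identify one. A test of baseline difference needs a group term, change over time needs a time term, and a difference in rate of change needs their interaction. With time coded 0/1, the treatment effect is that interaction. Under an identity link with complete pairs it is exactly the difference between arms in mean change.

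Because the baseline is measured before allocation, any observed baseline difference between arms is chance. A free group term subtracts that chance difference in full from the follow-up difference. An efficient analysis subtracts only the part that predicts follow-up. The between-arm baseline test likewise asks a question that randomization has already answered.

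What is at stake is precision in a small trial. The SAP justifies its relaxed threshold partly by the cost of a Type II error, yet it leaves unused some information that the collected baseline values could supply. The affected measures bear on hypothesis 4 (CTS2, for partner violence) and hypothesis 2 (ATSS and physiological arousal).

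**Working it through.** **Inputs from the documents.** The protocol states: "Sixty fathers, their female co-parent and youngest child will be recruited to participate in the study". Allocation is by urn randomization with no ratio given. The significance threshold is .10, with sidedness not stated. The documents give no power figure, effect size, SD, dropout rate or baseline-to-follow-up correlation, so there is no planned figure to reproduce.

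**Assumptions.** 30 fathers per arm, two-sided testing, complete pairs, an effect of d = 0.5 in follow-up SD units, and a range of correlations rho.

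**Step 1: variances.** Use an identity link, follow-up SD 1 and baseline SD k.
- Difference in change: factor 1 + k² − 2·rho·k.
- Adjusted for baseline: factor 1 − rho².
- Ratio: 1 + (k − rho)²/(1 − rho²), which is never below 1.

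At k = 1 the ratio is 2(1 − rho)/(1 − rho²) = 2/(1 + rho).

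**Step 2: power.** The standard error is s·√(2/30) = 0.258·s, with s the square root of the factor. Power is Φ(0.5/SE − 1.645). For example, at rho = .5:
- planned: s = 1, 0.5/0.258 = 1.936, Φ(0.291) = .61;
- adjusted: s = √.75 = .866, 0.5/0.2236 = 2.236, Φ(0.591) = .72.

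Results with k = 1:

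| rho | Variance ratio, 2/(1+rho) | Fathers giving equal precision if adjusted, 60(1+rho)/2 | Power, planned | Power, adjusted |
|---|---|---|---|---|
| .3 | 1.54 | 39 | .50 | .65 |
| .5 | 1.33 | 45 | .61 | .72 |
| .7 | 1.18 | 51 | .80 | .86 |
| .9 | 1.05 | 57 | .996 | .997 |

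Ignoring baseline altogether (s = 1) gives power .61. With equal variances, the planned test is therefore weaker than a follow-up-only comparison whenever rho is below .5. At rho .5, the adjusted test at two-sided .05 also has power .61, about what the planned test has at .10.

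**Step 3: sensitivity to the variance ratio.** If the baseline SD is 0.8 of the follow-up SD, the ratio at rho .5 is 1 + (0.3)²/.75 = 1.12, and at rho .7 it is 1 + (0.1)²/.51 = 1.02. If the baseline SD is 1.25 times the follow-up SD, the ratio at rho .5 is 1 + (0.75)²/.75 = 1.75. The loss can be much smaller or larger than in the table.

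**Step 4: simulation.** With 600 replicates per correlation, an identity link and exchangeable working correlation, the free-baseline interaction equalled the difference in mean change in every replicate. The constrained GEE had 0.66, 0.79 and 0.81 of its variance at rho .3, .5 and .7, against 0.65, 0.75 and 0.85 in theory. Follow-up adjusted for baseline agreed to within 0.002. One assumed log-link count scenario gave 0.72 for the constrained GEE. Mean estimates agreed across methods, so the difference is in precision and not in bias.

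**Step 5: the choice of remedy matters for binary outcomes.** Take 50% with the event at baseline, then 50% v 25% at follow-up, with latent correlation .8. The marginal log odds ratio is ln(.25/.75) − ln(.50/.50) = −1.10. In simulation the constrained GEE recovered about −1.10. A logistic model with baseline as covariate gave about −1.62, because it estimates a conditional odds ratio.

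**Step 6: working correlation.** Under working independence and an identity link, the constrained model's treatment estimate reduces to the plain difference in follow-up means; in simulation the two matched to rounding error. The gain therefore needs a non-independence structure. The SAP names none.

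**The case against.** The planned test is valid: under randomization the interaction is unbiased, and a conventional GEE is defensible in a pilot seeking feasibility and an intervention signal. That stands, and it limits the point to efficiency. A reader might infer that the trial's treatment estimates are biased; nothing in the documents supports that.

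The size of the loss is conditional. No correlation, SD or effect size is given, the equal-variance formula does not describe skewed counts, and all figures assume 60 complete pairs. This stands too. The protocol (Equipment) makes heart-rate and skin-conductance recording optional, so incomplete pairs are foreseeable for that outcome.

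A reader might also infer that the loss falls on the principal violence scale and on the sole measure of hostile cognition, or that Type II error is the plan's overriding concern. The documents say none of this. They do not rank the CTS2 above the other violence outcomes, and the IPV timeline follow-back has no baseline mark and is unaffected. Table 1 does not map instruments to constructs, and Expected Results names the STAXI and DERS alongside the ATSS. The SAP gives Type II error as one of two reasons for its threshold.

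Nor is the free baseline confined to two-measurement outcomes. The same model structure applies to outcomes with a baseline and two or more later visits, although the figures above do not carry over to them.

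**Conclusion.** The point holds as a matter of efficiency. For the CTS2, court and arrest records, ATSS with heart rate and skin conductance, and the two quizzes, the SAP implies a free baseline by arm that the design makes unnecessary. Under the stated assumptions the variance is inflated by 18% to 54% for rho from .7 down to .3, and adjustment adds 6 to 15 percentage points of power at d = 0.5. The gain is about nil near rho .9 and close to nil wherever the ratio of baseline to follow-up SD is near rho. Confidence is high in the direction and in the reading of the model, and lower in the size. The change is worth making, but the planned analysis is not invalid without it.

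**What to change.** - For every outcome with a baseline and one later measurement, and for all links, keep the GEE but fit time and group-by-time terms with no group main effect, so that the arms share a baseline mean. Retain facility. State a working correlation other than independence, such as exchangeable. This keeps the marginal estimand and the fathers who have only one measurement.
- For continuous identity-link outcomes with complete pairs, follow-up adjusted for baseline is an alternative with essentially the same result. It should not be substituted for dichotomous outcomes, where the estimand changes, or for incomplete pairs, where it drops fathers.
- Replace the between-arm baseline test with descriptive baseline values by arm.
- Consider the same constraint for outcomes with a baseline and two or more later measurements, so that the plan treats baseline consistently.

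The cost is SAP wording and a changed model specification; no new data are needed. The SAP is dated 3/25/2019 and written in the past tense. If the analyses have already been run, report the constrained model as a labelled supplementary analysis beside the planned one, not in place of it.

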Official Study Title:

Intimate Partner Violence and Fatherhood Intervention in Residential Substance Abuse Treatment

NCT Number: NCT02979262

Date Last Modified: 8/14/2017

IRB approval: 8/27/2018

Project Title

Intimate Partner Violence and Fatherhood Intervention in Residential Substance Abuse Treatment

Study Rationale and Background Information

Substance use and intimate partner violence (IPV) are two severe problems that often co-occur (Centers for Disease Control & Prevention, 2013; Centers for Disease Control, 2012; Shorey, Stuart, & Cornelius, 2011) and can lead to poor parenting behaviors (Gustaffson & Cox, 2012; McMahon, Winkel, & Rounsville, 2008). Current treatments for co-occurring substance abuse and IPV are lacking ([name], 2013). This study will test initial efficacy of a novel intervention for IPV and substance use among fathers in residential substance abuse treatment: Fathers for Change compared to a standard parenting intervention.

Research Hypotheses

This initial pilot will assess the feasibility, acceptability, and intervention signal of Fathers for Change compared to a Parent Education Condition within a residential treatment center for substance dependent men. We will test the following specific hypotheses:

1. Fathers in the Fathers For Change (FFC) group will have comparatively greater completion rates in both the residential and aftercare components of the program compared to fathers in the Dads 'n' Kids (parenting education-PE) program.
2. Fathers in the FFC group will exhibit greater improvement in hostile cognitions, emotion regulation and physiological arousal at the time of residential treatment discharge (12 weeks) and following aftercare sessions (16 weeks) than fathers in the Dads 'n' Kids group.
3. Men in the FFC group will experience comparatively less substance abuse relapse at the 3 month-follow-up than in the Dads 'n' Kids group.
4. Men in the FFC group will report fewer intimate partner violence (IPV) incidents and CM risk behaviors at 24 week follow-up than fathers in the Dads 'n' Kids group.
5. Exploratory Hypothesis: The relationship of Intervention (FFC versus PE) to substance abuse relapse, IPV, and child maltreatment risk behavior (at 24 week follow-up) will be mediated by reductions in hostile cognitions and emotion regulation (measured at 16 weeks).

Study Design

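### For DERS, STAXI, PRFQ and father-reported AAPI the SAP states only a baseline gap and a slope between arms, with no difference at the weeks that H2 and H4 name, and its free baseline costs power

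*SAP*

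**What the plan says.** The SAP has one section, Data analysis Plan. For repeated outcomes it uses GEE to test "between group differences in baseline values, within-group change over time, and between-group differences in the rate of change", and it applies this to "primary and secondary outcomes measured two to five times from randomization" through follow-up. Time is coded in two ways. With two waves, "When there were only two measurements, time was dummy coded to represent the first and second measurements". With more, "When there were three or more measurements, time was coded as a continuous variable representing weeks from randomization". No quadratic, spline or categorical-visit term is mentioned. The SAP also says that end-point outcomes were analyzed, but does not say what they are.

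The protocol's Research Hypotheses are tied to weeks. H2 asks for greater improvement in hostile cognitions, emotion regulation and arousal at weeks 12 and 16. H3 asks for "comparatively less substance abuse relapse at the 3 month-follow-up". H4 asks for fewer IPV incidents and "CM risk behaviors at 24 week follow-up". Expected Results, item 2, also expects lower STAXI and DERS scores after the intervention and at week 24.

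Table 1 marks DERS and STAXI at weeks 0, 12, 16 and 24, and PRFQ and father-reported AAPI at weeks 0, 16 and 24.

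**The concern.** The hypotheses ask how far apart the arms are at given weeks. The listed tests ask whether the arms differ at week 0 and whether they diverge at a constant weekly rate. The two questions agree only if the between-arm gap grows in a straight line from zero. If it does not, anyone who uses the fitted line to answer H2 or H4 reports the wrong size of difference.

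The second issue is separate. The model gives the arms their own baseline means and tests them against each other. In a randomized trial the true baseline means are equal, so this spends information that could sharpen the treatment comparison. With 60 fathers that loss matters.

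**Working it through.** **Outcomes covered.** Counting marks in Table 1, the continuous-time rule applies to DERS and STAXI (four waves) and to PRFQ and father-reported AAPI (three). STAXI is tied to H2 through Expected Results, item 2. Rumination also has three waves (0, 12, 16), but no hypothesis names it. ATSS with heart rate/skin conductance, CTS2 and court records have two waves and are dummy coded. So is mother-reported AAPI, because Study Design gives co-parents only a baseline and a 3-month follow-up assessment.

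**Assumptions.** The plan gives no power figure, effect size or correlation, so there is nothing to reproduce. I assume 30 per arm (60 fathers), a 0.6 SD gap, identity link, exchangeable correlation ρ = 0.5 (range 0.3 to 0.7), two-sided .10 and no dropout. The between-arm difference vector d then has covariance (2/30)R.

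**Shape distortion, DERS/STAXI.** For t = 0, 12, 16, 24 the mean is 13 and Sxx = 300. Set the true gap to 0, 1, 1, 1 (plateau from week 12).
- Slope: (12 + 16 + 24 − 13×3)/300 = 13/300 = 0.0433 per week.
- Week-0 term: 0.75 − 13×0.0433 = 0.187.
- Fitted gaps: 0.71 at week 12, 0.88 at week 16 and 1.23 at week 24, against a true 1.00 each time.

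For PRFQ/AAPI (t = 0, 16, 24; mean 13.33, Sxx = 298.67) with a plateau from week 16, the slope is 13.33/298.67 = 0.0446 and the week-0 term 0.071. The fitted gaps are 0.79 and 1.14 at weeks 16 and 24. A linear gap is recovered exactly.

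**Cost of the free baseline, DERS/STAXI.**
- SAP slope: SE = √[(2/30)(1−ρ)/Sxx] = √(0.0333/300) = 0.01054. Linear growth to 0.6 at week 24: 0.025/0.01054 = 2.37, power 77% (64–92% over the ρ range). Plateau: 0.026/0.01054 = 2.47, power 79% (67–94%).
- Common-baseline slope: estimate t′R⁻¹d / t′R⁻¹t, variance (2/30)/(t′R⁻¹t). At ρ = 0.5, t′R⁻¹t = 2(976 − 0.2×52²) = 870.4, so SE = 0.00875. Linear: 0.025/0.00875 = 2.86, power 89%. Plateau: t′R⁻¹d = 2(31.2 − 18.72) = 24.96, slope 0.0287, ratio 3.28, power 95%.

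The common baseline restores power but not the visit estimates. Its fitted gaps under the plateau are 0.57, 0.76 and 1.15 of the truth.

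**Does visit coding add power?** This compares the slope with a joint 2-df test of weeks 12 and 16 (critical value 4.605), with the same baseline handling on both sides. The noncentrality is e′V⁻¹e, where e holds the two visit differences. For change from baseline, V = (2/30)[[1, .5], [.5, 1]]. With baseline adjustment, V = (2/30)[[.75, .25], [.25, .75]]. The plateau gives 7.2 and 10.8; linear growth (gaps 0.30 and 0.40) gives 2.6 and 3.825.

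| True effect | Unadjusted: slope | Unadjusted: joint | Adjusted: slope | Adjusted: joint |
|---|---|---|---|---|
| Linear | 77% | 40% | 89% | 53% |
| Plateau from week 12 | 79% | 77% | 95% | 91% |
| Half faded by week 24 | 41% | 77% | 71% | 91% |
| Gone by week 24 | 12% | 77% | 31% | 91% |

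For PRFQ/AAPI the week-24 contrast has 75% unadjusted, against a slope of 77% (linear) and 81% (plateau). Adjusted, it has 85% against 89% and 94%.

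**Uncertain cases.** "Timeline follow-back for IPV" and its substance-use counterpart are marked monthly and at weeks 12, 16 and 24, with no baseline mark, so a week-0 term would be an extrapolation. If TLFB were taken at weeks 4, 8, 12, 16 and 24 (assumed) and a 0.6 SD benefit were present from the first one, the slope would be zero (10% rejections, the nominal rate) and the week-0 term would be significant in 77% of trials. Urinalysis has five occasions if monthly means weeks 4 and 8, but six if week 12 counts, which is above the SAP's maximum. The SAP does not say how relapse is built from either.

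**The case against.** The best defence is that a slope is a legitimate reading of greater improvement, uses all waves in one test, and has equal or better power than visit contrasts under linear growth or a plateau. Expected Results, item 2, fits both shapes, and nothing in the documents predicts fading. All of this stands. It means the slope should stay.

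Three stronger readings are tempting, and the documents do not support them.
- *The SAP never estimates the named-week differences.* It says that end-point outcomes were analyzed, and these might include such comparisons. A week-t gap can also be computed from the model as group term plus t times interaction, valid if linear. What can be said is that the plan does not state them.
- *Visit contrasts should decide H2 and H4 because they are more powerful.* Setting the adjusted joint test (91%) beside the unadjusted slope (79%) suggests this, but that gain comes from baseline adjustment. Like for like, visit coding gains only under fading.
- *Treatment benefit will be mistaken for baseline imbalance.* For DERS/STAXI under a plateau the week-0 term reaches p<.10 in 13.5% of trials against 10% nominal, and for PRFQ/AAPI in 10.5%. The risk is larger for TLFB, but only if the arms separate very early. The protocol's Risks section makes that less likely, since the men are in residence for most of the study.

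**Conclusion.** The point holds for DERS, STAXI, PRFQ and father-reported AAPI. The plan states no between-arm difference at the weeks that H2 and H4 name, and it leaves end-point outcomes undefined. Differences read off its straight line would be about 29% too small at week 12 and 23% too large at week 24 if a DERS/STAXI effect plateaus from week 12. These ratios do not depend on effect size or correlation, given complete data and an identity link.

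The free baseline costs 12 points of slope power if the effect is linear (77% against 89%) and 16 under a plateau (79% against 95%). These figures rest on the assumed 30 per arm, 0.6 SD, ρ = 0.5 and no dropout. The time coding is a reporting gap and does not make the test invalid. TLFB and urinalysis are possible cases only, and the two-wave outcomes are not affected.

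**What to change.** 1. Where a baseline was collected, constrain the arms to a common baseline mean or adjust for baseline, and drop the between-arm baseline test for outcomes.
2. Keep the slope test. For these four outcomes also fit visit as categorical and report baseline-adjusted group differences with intervals at weeks 12 and 16 (H2) and week 24 (H4, and the DERS/STAXI expectation in Expected Results). The SAP is written in the past tense, so label these as added later. Do not count them as extra .10 tests: under the null, simulation at ρ = 0.5 gives about 18% rejection for slope or joint test, and about 15% for AAPI slope or week-24 contrast. Do not read week-specific differences off the line.
3. Define end-point outcomes. If TLFB is modelled with continuous time, do not call its extrapolated week-0 term a baseline difference, and report the week-24 difference that H3 and H4 name.

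The cost is SAP wording and re-run models on data already scheduled for collection. Each categorical-visit model has two (three waves) to four (four waves) more parameters, and intervals at single visits are wider.
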